20. Archival tumor tissue samples will be collected at screening as long as no anticancer therapy was administered since the sample was collected. Fresh tumor tissue sample will only be collected if a patient qualifies for the study based on all other entry criteria and archival tissue is not available or not collected after the last anticancer therapy.

All Patients (optional): Additional tumor tissue samples may be collected for patients undergoing medical procedures including resection of metastases while on study or for patients that have disease progression if the patient consents and these samples will be used for further molecular testing of the cancer while treated with study drug.

21. CT scans of the pelvis, abdomen, and chest will be performed at screening (within 21 days of Cycle 1 Day 1). Subsequently, CT scans of the pelvis and abdomen will be performed every cycle through and including Cycle 4, and then every other cycle thereafter (ie, Cycle 6, 8, 10, etc.). CT scans of the chest will only be performed subsequently if the patient had lung metastases at screening or in case of lung symptoms (per the Investigator's discretion). Radiologic imaging may be performed up to 7 days prior to the corresponding study visit or post dose at the study visit. An initial indication of a partial or complete response based on investigator assessment must be confirmed ≥ 4 weeks later. MRI scans of the abdomen/pelvis and CT scan without contrast of the chest can be used for patients who are allergic to radiographic contrast media. Additionally, for patients whose local regulatory authority and/or ethics committee has not approved use of CT scans, MRIs may be used. Throughout the study, the same assessment technique must be used. Ultrasound scanning is not an acceptable substitute for CT scanning. See [Section 6.10.1](#) for further details.

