6.3. Treatment Period

Patients will be randomized in the study after confirmation of all eligibility criteria. The first dose of study drug must be administered in the clinic on Cycle 1 Day 1. Study visits during the Treatment Period will occur as shown in [Table 1](#) (schedule of assessments) and [Table 2](#) (schedule of assessments for crossover). Patients will be outpatients during the Treatment Period. All visits must occur within the windows specified.

Patients who prematurely discontinue study drug must return for an EOT Visit within 7 days after the last dose of study drug.

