9. STATISTICAL CONSIDERATIONS

9.1. Determination of Sample Size

The sample size selection of approximately 120 patients (n=80 DCC-2618, n=40 placebo) was based on considerations for powering of the primary endpoint, key secondary endpoint, detection of rare safety events and overall exposure to DCC-2618, and assuming 15% patient dropout. Patients will be randomized in a 2:1 ratio of DCC-2618 versus placebo.

This sample size [105 patients (n=70 DCC-2618, n=35 placebo) with 90 events (55 DCC-2618, 35 placebo) at the final analysis] will have at least 90% power to detect a difference in PFS between DCC-2618 and placebo assuming a median PFS of 4.5 months for DCC-2618 and 1 month for placebo. Moreover, this assumes 9 months of uniform recruitment and 6 additional months of follow-up (total patient follow-up of 15 months).

Furthermore, 105 patients (n=70 DCC-2618, n=35 placebo) will have approximately 80% power to detect a 0.2 difference in ORR assuming that the ORR for DCC-2618 = 0.22 and the ORR for placebo = 0.02.

In addition, a minimum sample size of 80 DCC-2618 patients allows adequate power to detect the incidence of rare safety events. A sample of 80 patients yields 95% probability that the study will reveal at least one occurrence of all safety events that occur in patients at a rate of 4.0% or greater. This in combination with the exposure to DCC-2618 from other studies conducted in this clinical program will meet the recommendations for overall exposure recommended by FDA.

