3.1 Statistical Analysis Periods

Based on the study design, two main analysis periods will be defined as follows:

- Double-blind treatment analysis period
 - from the randomization date to the last follow-up date
 - if a patient did not have disease progression based on independent radiologic review or
 - if a placebo patient did not cross over to DCC-2618 treatment or
 - if a patient was initially treated with DCC-2618 and did not continue to receive DCC-2618 at 150mg QD or escalate to 150mg BID after disease progression based on independent radiologic review from the randomization date to the first disease progression date if a patient was initially treated with DCC-2618 and continued to receive DCC-2618 at 150mg QD after disease progression based on independent radiologic review
 - from the randomization date to the day immediately before the first dose of DCC-2618 150mg BID if a patient escalated to DCC-2618 150mg BID after disease progression based on independent radiologic review
 - from the randomization date to the day immediately before the first dose of DCC-2618 150mg QD if a patient crossed over from placebo to receive DCC-2618 at 150mg QD after disease progression based on independent radiologic review
- Open-label analysis period
 - from the day immediately after the first disease progression based on independent radiologic review to the last follow-up date if a patient was initially treated with DCC-2618 and continued to receive DCC-2618 150mg QD after disease progression based on independent radiologic review
 - from the first dose date of DCC-2618 150mg BID to the last follow-up date if a patient was initially treated with DCC-2618 and escalated to DCC-2618 150mg BID after disease progression
 - from the first dose date of DCC-2618 150mg QD to the last follow-up date if a patient crossed over from placebo to receive DCC-2618 150mg QD after disease progression based on independent radiologic review

The primary efficacy endpoint, progression-free survival, will be defined and analyzed only during the double-blind treatment analysis period.

Overall survival will be defined and analyzed throughout patients' entire on study period. The data cut-off for the primary analysis will occur when 90 PFS events have occurred. It is expected that the primary analysis will occur approximately 6 months after the last patient is enrolled into the trial.

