As of the primary efficacy analysis, the evaluation of the efficacy and safety of DCC-2618 against the placebo will be mainly based on the data collected during the double-blind treatment analysis period. The analysis during this period will be detailed in [Sections 3.2 to 10.10](#).

For data collected during the open-label analysis period and entered in the database by the data cut-off date or at the final database lock, statistical analysis will be described in [Section 11](#).

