8.3.5 Quality of Life

Quality of life (QOL) will be based on European Organisation for Research and Treatment of Cancer Quality of Life Questionnaire for Cancer 30-item (EORTC-QLQ-C30) and the EuroQol 5-Dimension 5-Level (EQ-5D-5L) questionnaires.

The EORTC-QLQ-C30 will be summarized by scale. In all scales, a high scale score represents a higher response level. The scoring for this questionnaire will be done in 2 steps.

1. Calculate the average of the items that contribute to the scale. This will be used as the raw score for the scale, and
2. Apply a linear transformation to standardize the raw score, so that scores range from 0 to 100.

Changes from baseline to Day 1 of Cycle 2 in EORTC-QLQ-C30 Role function and Physical function will be compared between the two treatment arms using analysis of covariance (ANCOVA) model with the stratification factors as factors. If Day 1 of Cycle 2 value is missing, then the change from baseline to the end of initial study treatment will be used in the analysis.

The EQ-5D-5L is a standardized measure of health status comprised of a descriptive system including five health-related QOL states (ie, mobility, self-care, usual activities, pain/discomfort, and anxiety/depression) and a visual analogue scale (VAS) of overall health. Each dimension is rated on a 5-point response scale indicating severity of problems, where 1 is “no problems”, 2 “slight problems”, 3 “moderate problems”, 4 “severe problems”, and 5 is “extreme problems”. The five questions are scored and together contribute to the EQ-5D-5L index (utility) score between 0 and 1 (1 being perfect health), which will be calculated using the developers’ algorithm based on country-specific reference score sets (Van Hout et al., 2012). Score sets are available for Denmark, France, Germany, Japan, Netherlands, Spain, UK, US and Zimbabwe. For countries in which no score set exists (Canada, Hungary, Israel, Romania, and Sweden) the closest neighboring country will be used as a proxy (EuroQol Group, 2015), eg, UK value set for Australia, France value set for Belgium, USA value set for Canada and Singapore, and Germany value set for Poland. If scale is missing for one of the dimensions, the index (utility) score will have a missing value.

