EQ-5D-5L will be summarized overall by number and percentage for each level of each dimension. For pain/discomfort and usual activities, the Cochran–Mantel–Haenszel test will be used to test the change in response scale at Day 1 of Cycle 2 from baseline between DCC-2618 and placebo. For EQ-5D-5L index (utility) score, an ANCOVA model with the stratification factors as factors will be used to compare the change at Day 1 of Cycle 2 from baseline between the two treatment arms.

The EuroQol visual analogue scale (EQ-VAS) is a measure of overall self-rated health status, used and analyzed separately from the index score. The EQ-VAS recorded the subject’s self-rated health on a 20 cm vertical VAS with endpoints labelled “the best health you can imagine” and “the worst health you can imagine.” The EQ-VAS score ranges from 0 to 100,

with higher scores indicative of better overall health. EQ-VAS will be summarized using continuous descriptive statistics. Change in EQ-VAS score at Day 1 of Cycle 2 from baseline between the two treatment arms will be tested with a t-test.

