8.5 Multiple Comparisons/Multiplicity

To control familywise type-I error, the hypothesis tests for treatment difference between DCC-2618 and placebo will be performed at two-sided 0.05 level of significance sequentially in the following order:

1. The primary endpoint PFS based on independent radiologic review
2. The key secondary endpoint ORR based on independent radiologic review
3. OS
4. QOL as determined by changes from baseline to Day 1 of Cycle 2 in EORTC-QLQ-C30 Role function and Physical function (each at 0.025 level of significance)

If any hypothesis test is not significant at $\alpha=0.05$ level, the subsequently listed analyses will be viewed as descriptive.

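### SAP 8.3.5 sets no time limit on the score that replaces a missing Cycle 2 Day 1 Role or Physical function value, so patients still on treatment can contribute much later scores (minor)

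*SAP*

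**What the plan says.** SAP 8.5 names the fourth step of the hierarchy as "QOL as determined by changes from baseline to Day 1 of Cycle 2 in EORTC-QLQ-C30 Role function and Physical function", each scale tested at 0.025. SAP 8.3.5 analyses both by ANCOVA with the stratification factors and adds one rule for a missing visit: "If Day 1 of Cycle 2 value is missing, then the change from baseline to the end of initial study treatment will be used".

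No other text limits that rule:

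- SAP 8.4 refers back to 8.1-8.3 for efficacy endpoints.
- SAP 3.2 maps unscheduled visits to scheduled ones where possible but gives no window for questionnaires.
- Protocol Table 18 deals with missing items, not a missing visit.

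Under Protocol 6.3, patients who discontinue early "must return for an EOT Visit within 7 days after the last dose of study drug", whenever that dose falls. Protocol Table 1 also schedules the QLQ-C30 at Cycle 1 Day 15 and at Day 1 of every later cycle. For the EQ-5D-5L index at the same visit, SAP 8.3.5 says "an ANCOVA model with the stratification factors as factors will be used to compare the change at Day 1 of Cycle 2 from baseline" and states no substitution.

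**The concern.** The hypothesis concerns week 4, but the substitute is tied to the end of treatment. For someone who stopped before Cycle 2 Day 1 the two are close. For someone still on treatment who missed the form, the gap is as long as treatment lasts, and the trial is designed so that treatment lasts longer on DCC-2618. Two things then differ by arm:

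- **Timing.** Later scores enter the DCC-2618 mean than the placebo mean.
- **Inclusion.** A patient still on initial treatment at the data cut has no end-of-treatment score and cannot be substituted. This will be mostly DCC-2618 patients.

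The rule also passes over nearer scores that the schedule already collects. At stake is whether the step-4 result, if the sequence gets that far, estimates the week-4 difference it names.

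**Working it through.** **Inputs from the documents.** Protocol 9.1 and SAP 2.3: "assuming a median PFS of 4.5 months for DCC-2618 and 1 month for placebo", 9 months of uniform recruitment plus 6 of follow-up, and 90 events (55 of 70 and 35 of 35). Protocol 5.2: 28-day cycles, so Cycle 2 Day 1 is 4 weeks after the start.

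**Assumptions.** Exponential PFS; initial treatment ends at the PFS event; 30.44-day months (4.35 weeks).

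**1. Reproduce the plan's event count.** With L = ln 2 / median, P(event) = 1 - (e^(-6L) - e^(-15L)) / (9L).

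- DCC-2618: 0.785 x 70 = 54.97
- Placebo: 0.9975 x 35 = 34.91
- Total: 89.9, matching the stated 55, 35 and 90.

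**2. Share still on treatment at week 4.** exp(-ln 2 x 4 / (median in months x 4.35)) = 0.868 on DCC-2618 and 0.529 on placebo. So 13.2% and 47.1% have an event by week 4.

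**3. When the substitute falls, for those on treatment at week 4** (simulated from the same inputs):

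| | DCC-2618 | Placebo |
|---|---|---|
| Median week | 17.3 | 8.3 |
| Mean week | 20.0 | 10.1 |
| None at the cut | 24.7% | 0.5% |

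Protocol Table 1, note 21, says "CT scans of the pelvis and abdomen will be performed every cycle through and including Cycle 4, and then every other cycle thereafter". If progression is instead read at those scans (weeks 4, 8, 12, then every 8), the medians are weeks 20 and 12, the means 22.5 and 13.0, and none exists for 28.6% and 1.0%.

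**4. Distortion under a steady drift.** The documents give neither missingness nor drift. Assume a share q of 5-20% missing among on-treatment patients and a drift d of 0.25-1 point per week, the same in both arms. Per arm:

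shift = on x q x (1 - none) x d x (mean week - 4) / (1 - on x q x none)

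- q = 0.05, d = 0.25: 0.132 - 0.040 = 0.09 points
- q = 0.20, d = 1: 2.18 - 0.65 = 1.54 points (about 2.18 - 0.65 before rounding)
- Scan-timed: 0.09 to 1.47 points

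If scores fall, this counts against DCC-2618.

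**5. Distortion under a one-off fall of 10-20 points at progression** (assumed). The current rule shifts the difference by 0.08 to 0.74 points against DCC-2618.

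**6. Scale.** With an assumed SD of 20 and 80 and 40 patients, the standard error is 20 x sqrt(1/80 + 1/40) = 3.9 points, and 1.54 / 3.9 = 0.4.

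**7. Same scenarios with Cycle 1 Day 15 as the substitute for on-treatment patients.** That score is 2 weeks early in both arms, so the distortion is 2 x d x q x (0.868 - 0.529). At q = 0.20 and d = 1 this is 0.14 points; at q = 0.05 and d = 0.25 it is under 0.01. Under a one-off fall at progression it is zero, because these patients had not progressed by either visit. No patient is lost if the Day 15 score exists.

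**8. Why simply barring late scores is not enough.** Early stoppers would keep their values while on-treatment patients lost theirs. With a 20-point fall and q = 0.20, the arm mean changes from -0.132 x 20 = -2.64 to -2.64 / (1 - 0.174) = -3.19 on DCC-2618, and from -9.43 to -9.43 / (1 - 0.106) = -10.54 on placebo. The difference moves by about 0.56 points in favour of DCC-2618.

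**The case against.** The strongest reply concerns weight. Patients on treatment at Cycle 2 Day 1 come to the site, receive drug there and complete the form on a tablet before seeing the investigator, so few forms should be missing. SAP 3.2 may recover some completed off-schedule. Step 4 is reached only after PFS, ORR and OS, and OS has no power statement. Every input to the size in points is assumed. A separate illustration with steeper declines (3-10 points per 28 days, SD 25) gave bias of 0.2 to 3.3 points against DCC-2618. Its rejection rates under no difference were 0.025-0.026 at 5-10% missing and 0.027-0.035 at 20%, against a nominal 0.025. All of this stands and is why the point is minor.

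The timing figures also rest on a proxy: toxicity stops and continued dosing after progression separate the end of treatment from the PFS event. That affects the exact weeks, not the absence of a limit.

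A reader might infer that the rule flatters DCC-2618. The documents do not support that: with falling scores it works the other way, and it favours DCC-2618 only if late scores improve. A reader might also infer that scores taken after crossover enter the comparison. SAP 3.1 ends the double-blind period for such patients "from the randomization date to the day immediately before the first dose of DCC-2618 150mg QD if a patient crossed over from placebo" and says the evaluation against placebo "will be mainly based on the data collected during the double-blind treatment analysis period", which largely excludes them.

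An end-of-treatment score may follow unblinding at reviewed progression. Requiring scores from before unblinding would be a poor remedy, however, because it would discard early stoppers' scores, more of them on placebo.

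**Conclusion.** The gap is real and minor. SAP 8.3.5 lets a week-4 test use scores from any later time for patients still on treatment, and on the plan's medians both timing and availability differ by arm (about week 17 against week 8; about 25% against 0.5% with no substitute). The likely effect is 0.1 to 1.5 points, at most about 0.4 of an assumed standard error, against DCC-2618 if scores fall. That range depends on assumed missingness, drift and SD, and on treatment ending at the PFS event. The rule is sound for patients who stop before Cycle 2 Day 1. The unsubstituted EQ-5D-5L analysis gives a partial check, but on another instrument and outside the hierarchy.

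**What to change.** Replace the sentence in SAP 8.3.5 with:

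> If the Cycle 2 Day 1 score is missing and the patient stopped initial treatment on or before scheduled Cycle 2 Day 1, the end-of-treatment visit score (within the protocol's 7 days of last dose) is used. If the patient was still on initial treatment at Cycle 2 Day 1, the end-of-treatment score is not used; the nearest scheduled score on initial treatment is used (Cycle 1 Day 15, or Cycle 3 Day 1 if Day 15 is missing). One sensitivity analysis uses multiple imputation by arm among on-treatment patients from the adjacent visits. Another uses no substitution.

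Early stoppers need no tighter day limit, since the protocol allows 7 days for that visit. A repeated-measures model split by treatment status is not needed either: patients off treatment have no Cycle 3 Day 1 form on initial treatment.

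The cost is a short SAP edit and one or two extra analyses, with no new data. Late scores are no longer used: at 5-20% missing, about 3 to 10 on DCC-2618 (80 x 0.868 x q x 0.753) and 1 to 4 on placebo (40 x 0.529 x q x 0.995). Most would be replaced by a Day 15 score. A patient with neither adjacent score stays missing in the main analysis.

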8.3.6 Disease Control Rate

Disease control rate (DCR) will be calculated and summarized with n and percentage. Disease control will be defined as having a response (complete or partial) or stable disease lasting at least 12 weeks. Other time points (6, 9, 12 months) may be added on an exploratory basis.

8.3.7 Duration of Response

Duration of response is defined as the time interval from the first assessment of confirmed CR or PR until the first disease progression or death. In the case that the PFS is censored, duration of response will be censored at the last evaluable progression-free radiologic assessment in an analogous manner.

Duration of response based on the independent radiologic review will be analyzed with Kaplan-Meier method using the 25th, 50th (median), and 75th percentiles and survival probability at pre-specified timepoints, each with associated 2-sided 95% confidence intervals. Duration of response based on the Investigator assessment will be analyzed in a similar fashion as well.

8.4 Handling of Missing Data

For the analysis of efficacy endpoints, handling of missing data has been specified in [Sections 8.1, 8.2, and 8.3](#).

Algorithms for imputing partial or missing dates are shown below in [Table 1](#). If a period determination cannot be made for an adverse event, it will be attributed to the randomized blinded period. AE end dates are imputed to facilitate calculation of AE duration.

Table 1 Imputation Rules for Partially Missing Dates

Variable	Missing Day	Missing Day, Month	Missing Day, Month, Year
Date of Last Therapy/Date of Initial Diagnosis	Assign 1	Assign January 1 if prior to date of informed consent, otherwise use date of informed consent	Missing (do not impute)
Adverse Event/Start Date	Assign first day of month unless it is the month of first dose of study medication. Otherwise, assign date of first dose of study medication or AE end date (if not missing) whichever is earlier	Assign January 1 unless the year is year of first dose of study medication. Otherwise, assign date of first dose of study medication or AE end date (if not missing) whichever is earlier.	Assign date first dose of study medication.
Adverse Event End Date	Assign the last day of the month or death date or data cut-off date (or end of study date), whichever is earliest.	Assign December 31 or death date or data cut-off date (or end of study date), whichever is earliest.	If ongoing, end date is missing. Otherwise, assign death date or data cut-off date (or end of study date), whichever is earlier.

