9.4. Procedures for Handling Missing, Unused, and Spurious Data

All available data will be included in data listings.

Algorithms for imputing partial or missing dates are shown in Table 17. If a period determination cannot be made for an adverse event, it will be attributed to the randomized blinded period, with missing dates imputed as explained in Table 18. Adverse event end dates are imputed to facilitate calculation of AE duration.

Table 17: Partial or Missing Date Algorithms

Variable	Missing Day	Missing Day, Month	Missing Day, Month, Year
Date of Last Therapy/Date of Initial Diagnosis	Assign 1	Assign January 1 if prior to date of informed consent, otherwise use date of informed consent	Missing (do not impute)
Adverse Event/Start Date	Assign first day of month unless it is the year/month of first dose of study medication. Otherwise, assign date of first dose of study medication or AE end date (if not missing) whichever is earlier.	Assign January 1 unless the year is year of first dose of study medication Otherwise, assign date of first dose of study medication or AE end date (if not missing) whichever is earlier.	Assign date first dose of study medication.
Adverse Event End Date	Assign the last day of the month or end of study date, whichever is earlier.	Assign December 31 or end of study date, whichever is earlier.	If ongoing, end date is missing. Otherwise, assign end of study date.

Table 18: Imputation Rules for Questionnaires

Questionnaire	Number of items missing < half	Number of items missing > half
EORTC-QLQ-C30	No imputation for missing	Impute missing values by using the average score from the patients with non-missing values from within the same randomization strata

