10.2 Adverse Events

Adverse events tables will summarize the number and proportion of patients overall and by treatment arm with an event by each system organ class (SOC) and preferred term (PT) for the Safety population. All tables will only include treatment emergent adverse events (TEAEs), where TEAEs are defined as any AE that occurs that occurs after administration of the first dose of study drug and through 30 days after the last dose of study drug. In the case of missing start and/or stop date, non-missing date parts will be used to determine if an AE is treatment-emergent or not. An AE will be categorized as TEAE if a determination cannot be made using the non-missing date parts as to when the event occurred relative to study drug administration. Adverse event toxicity grade will be classified using the National Cancer Institute Common Terminology Criteria for Adverse Events (NCI-CTCAE) Version 4.03 criteria. For incidence summaries, a missing toxicity grade of a TEAE will be conservatively imputed as severe; for a TEAE missing causal relationship to study treatment, a causality of “related” will be assigned. Listings will include all reported AEs, flagging events that were TEAEs and displaying missing severity grades and causalities as they were entered in the clinical database.

An overall summary of the number of subjects with TEAEs as well as the number of event will be presented, including the number and percentage of subjects with any TEAEs, treatment-emergent serious adverse events (SAE), drug-related TEAEs and TEAEs leading to treatment discontinuation, study discontinuation, and death.

The number and percentage of patients reporting TEAEs, as well as the number of events, in each treatment group will be tabulated by SOC and PT; by SOC, PT, and maximum severity. If a patient has multiple occurrences of the same SOC and PT, then the patient will be counted only once for the SOC and PT using the most severe occurrence for the summarization by maximum severity. Presentation by SOC and PT will display SOC sorted alphabetically and PT by descending frequency within SOC.

TEAEs and drug-related TEAEs will be summarized by PT by descending frequency. Treatment-emergent SAEs, TEAEs leading to study treatment discontinuation and study discontinuation, and treatment-emergent SAEs leading to death will be summarized by SOC, PT, and treatment arm.

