11.5 Safety Analysis

Exposure to DCC-2618 will be summarized by analysis sub-periods. The duration of DCC-2618 in weeks, total dose, average daily dose, and relative dose intensity will be displayed using continuous descriptive statistics. In addition, the number and percent of patients in categories by treatment duration and patients with a dose increase, reduction, and interruption will be summarized.

All the AEs and the other safety data collected during the open-label analysis period will be analyzed. All the AEs in the open-label analysis period will be analyzed as TEAEs.

TEAEs and the other safety endpoints will be analyzed by treatment groups as defined by patients' initial treatment in the double-blind treatment period, for all patients who entered in the open-label analysis period overall and separately for each sub-period.

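### For placebo patients who cross over, SAP 3.1 and SAP 8.4 (Table 1) can place DCC-2618 adverse events in the placebo column; minor, with no net bias shown

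*SAP*

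**What the plan says.** **Periods.** SAP 3.1 splits follow-up into a double-blind and an open-label period. It says the evaluation against placebo "will be mainly based on the data collected during the double-blind treatment analysis period". The double-blind period runs to last follow-up if any one of several conditions, joined by 'or', is met. The first condition is having no progression by independent radiologic review; the second is a placebo patient not crossing over. The bullets that end the double-blind period just before the first DCC-2618 dose, and start the open-label period on that dose, apply to crossover after independently reviewed progression. Protocol 9.7 adds another route: once the primary PFS result is known, remaining placebo patients may cross over, with no progression condition.

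**Incomplete AE dates.** SAP 8.4 sets the default "If a period determination cannot be made for an adverse event, it will be attributed to the randomized blinded period". Table 1 gives the start-date rules:
- Day missing: "Assign first day of month unless it is the month of first dose of study medication".
- Day and month missing: 1 January, unless the year is that of the first dose.
- Everything missing: "Assign date first dose of study medication".

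In the first-dose month or year, the first-dose date is used (or the AE end date if earlier). Protocol Section 5 counts placebo as study drug and SAP 3.3 ties the first dose to Cycle 1 Day 1. SAP 11 lists no exception for AE dates in the open-label period.

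**Tables.** SAP 4.2 bases safety analyses on the treatment the patient took. SAP 11.5 groups open-label AEs by "initial treatment in the double-blind treatment period, for all patients who entered in the open-label analysis period".

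**The concern.** In a placebo patient who crosses over, only the period label separates events that began on placebo from events that began on DCC-2618, because the open-label tables are also grouped by the initial arm. Two rules can set that label wrongly.

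- **SAP 3.1.** For crossover without independently reviewed progression, time on DCC-2618 stays in the double-blind period. This affects even fully dated AEs.
- **SAP 8.4 and Table 1.** No rule refers to the first DCC-2618 dose after crossover. An AE that began on DCC-2618 but has an incomplete start date can be given a date before crossover and be counted under placebo.

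At stake is the accuracy of the placebo column in a small arm of about 40 patients, in the tables on which the safety comparison mainly rests.

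**Working it through.** The plan gives no figure for either rule, so there is nothing to reproduce first.

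**A. SAP 3.1, crossover without progression**

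1. Such a patient meets the first double-blind condition (no independently reviewed progression), so the period runs to last follow-up.
2. The patient does not meet either crossover bullet, since both require progression.
3. DCC-2618 time therefore counts as double-blind.

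How many patients: inputs from SAP 2.3 are 35 evaluable placebo patients, median PFS 1 month, and 9 months of uniform accrual plus 6 months of follow-up. With exponential PFS and λ = ln 2 / median, the event-free share at month 15 is

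p = (e^(−6λ) − e^(−15λ)) / (9λ)

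- Median 1 month: (0.015625 − 0.000031) / 6.238 = 0.0025, and × 35 = 0.09 patients.
- Median 2 months (assumed): (0.125 − 0.005524) / 3.119 = 0.0383, and × 35 = 1.34 patients.

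With 40 placebo patients the figures are 0.10 and 1.53. This crossover is possible only after the primary result, so the primary-analysis tables are untouched.

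**B. Table 1, incomplete start dates**

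Worked example (assumed dates): first placebo dose 4 June 2018, crossover 10 July, true onset 20 July. Day missing gives 1 July; day and month missing gives 4 June; fully missing gives 4 June. All three precede crossover, so all three count under placebo.

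Conditional shares, assuming crossover is equally likely on any day of the year and onset is uniform over the first W days on DCC-2618:

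- *Day missing.* An AE is misplaced if it starts in the crossover month and crossover was not on the 1st. Summed over a 365-day year, the eligible days from crossover to month end are 7 × 465 + 4 × 435 + 378 = 5,373, or 14.72 per crossover date. The share is 14.72 / W for W = 84 or 168. For W = 28, capping at 28 days gives 5,348 / 365 = 14.65.
- *Day and month missing.* An AE is misplaced if it starts in the crossover year and crossover was not on 1 January. The share is 1 − (W − 1) / (2 × 365) − 1/365.
- *Fully missing.* Always misplaced.

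| Missing part | W = 28 | W = 84 | W = 168 |
|---|---|---|---|
| Day | 52% | 17.5% | 8.8% |
| Day and month | 96% | 88% | 77% |
| All | 100% | 100% | 100% |

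Simulation with crossover 28, 42 or 56 days after first dose gives the same values. In the DCC-2618 arm, with open-label start after an exponential time of median 4.5 months (minimum 28 days), the shares agree within 0.2 points. There, open-label events move into the blinded DCC-2618 column.

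**C. Would testing the known date parts first change anything?**

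Table 1 imputes the earliest on-treatment date that the known parts allow. If that date falls in the open-label period, the known parts had already settled the matter. If it falls earlier, the AE is either truly earlier or unsettled, and the default sends unsettled AEs to the blinded period. An end date can only confirm onset before crossover. Enumeration with end dates unknown and known found the same period under both approaches for every AE.

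**D. Is there a better single default?**

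Under a constant AE rate from first placebo dose, about 50% of unsettled missing-day AEs in crossover patients began before crossover. If end dates are known and mean AE duration is 14 days (assumed), the figure is about 35%. Neither assignment is right for all of them.

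**E. Effect on one table row**

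One newly counted patient adds 1/40 = 2.5 points (placebo) or 1/80 = 1.25 points (DCC-2618), and only if that patient has no other blinded-period event of that term.

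**The case against.** The strongest reply is that the default is pre-specified in both documents, applies to both arms, and feeds a descriptive analysis: Protocol 9.8.6.1 plans no AE testing, and listings keep every event. AEs are collected continuously, with regular site visits after crossover, and serious events and events of special interest are reported within 24 hours of awareness. Nothing shows that even one AE would be affected, and the 96% and 100% apply only to dates missing at least the month. On SAP 3.1, the condition about not crossing over, and SAP 11.1, suggest that crossover was meant to end the double-blind period. All of this stands, and it is why the point is minor. It does not remove the literal text of SAP 3.1 or the conflict with SAP 4.2.

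Three stronger readings are tempting, but the documents do not support them:

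- **That the rule biases the safety comparison in favour of DCC-2618.** A reader might infer this from the placebo column alone. Both columns can gain events, the shifts partly offset, and the number of incomplete dates is unknown.
- **That the missing safeguard is a date-part test.** SAP 10.2 says that "non-missing date parts will be used to determine if an AE is treatment-emergent or not", and a reader might infer that the same test for the period would correct the assignments. Working C shows it gives the same result as Table 1 plus the default. For the same reason, the lack of a stated test for when the period cannot be determined has no effect on the tables.
- **That the date rules themselves are missing.** Protocol 9.4 says "with missing dates imputed as explained in Table 18", which is the questionnaire table. This is a clerical slip: the date rules are in Protocol Table 17, and SAP 8.4 points correctly to its own Table 1.

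**Conclusion.** Minor, in two parts.

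(a) SAP 3.1 is wrong as written for placebo patients who cross over without independently reviewed progression. The expected number is about 0.1 of 35 at the planned 1-month median and 1.3 at an assumed 2-month median. This rests on exponential PFS and the planned 15-month timeline, although the cut-off is in fact set by 90 events. Only tables after the primary analysis are affected.

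(b) SAP 8.4 and Table 1 put every AE of unsettled period in the blinded period, so some DCC-2618-onset AEs can appear under placebo, against SAP 4.2. The conditional shares rest on assumed onset windows. The number of such AEs cannot be obtained from the documents and may be small. Confidence is high in what the text does; no effect on the trial's safety conclusions is demonstrated.

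**What to change.** 1. **SAP 3.1.** For any placebo patient who crosses over, with or without progression, end the double-blind period the day before the first DCC-2618 dose and start the open-label period on that dose date.
2. **SAP 8.4 / Table 1.** Keep the default for the main table. Count, by arm, the AEs whose known date parts do not settle the period. The boundary is the first DCC-2618 dose for placebo crossover patients, and each patient's own open-label start under SAP 3.1 for the DCC-2618 arm. Show AE incidence with these AEs assigned to the blinded period and again to the open-label period, in the same way for both arms.

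The cost is a few words in SAP 3.1, a flag in the derivation code and one extra descriptive table. Neither display replaces the other, since neither assignment is right for every unsettled AE. No clinical procedure or data collection changes.
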